11.2 Screening and Enrolment

The heart failure clinic database will be screened during the study dates for eligible participants. Any eligible participants will then be included in the study, with only the relevant clinical data being recorded. Patients will be anonymised, with a separate document detailing pseudonymisation. No personally identifiable data will be included in the analysis or results.

11.3 Randomisation

N/A

11.4 Study Assessments

All data will be collected retrospectively from the heart failure clinic database at QAH. Data will be collected on: weight, number of hypertensive medications prescribed, presence of AF or not, presence of pulmonary hypertension or not, age and filling pressure. These are the factors that make up Reddy et al. (2018) H2FPEF score. In addition the patient's ejection fraction and BNP will also be recorded as a measure to determine HFpEF diagnosis. All data will be anonymised and recorded on a Microsoft Excel spreadsheet, with a separate document documenting the pseudonymised data. All data will have been routinely collected as part of the heart failure patient pathway:

- Echocardiography - A non-invasive ultrasound test which takes approximately 30 minutes and has no radiation risk. Echocardiogram results will be used to ascertain pulmonary pressure and diastolic filling pressure. This will have been performed routinely as part of the heart failure patient pathway at QAH. All scans will have been performed on GE Healthcare Vivid echocardiography machines by a trained sonographer from the Cardiac Investigations Unit at QAH. A standard operating procedure exists for performing echocardiogram. In accordance with local practice personal protective equipment is worn for this test. ECG electrodes and ultrasound gel can be a potential risk to the patient with regards to dermatological reaction/sensitivity, however both are hypoallergenic substances.
- 12-lead electrocardiogram (ECG) - A non-invasive test of the electrical conduction of the heart assessing heart rate and rhythm. ECG results will be used to determine if the patient is in AF or not. All ECG will have been recorded with the use of the hospitals standard machine (MAC 1200, GE Healthcare). All tests will have been

performed by trained staff within the Cardiac Investigations Unit at QAH. Standard operating procedures are followed to perform ECG. ECG will have been performed routinely as part of the heart failure patient pathway at QAH.

- Weight - Using a standard trust scale (Marsden Weighing Company, UK)
- Age and Number of hypertensive medications taken - Assessed from patient records

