7.2 Secondary Objectives

The investigator's secondary objectives are to:

- Investigate if H2FPEF overestimates HFpEF diagnosis on the patient population when compared against known BNP levels.
- To evaluate if H2FPEF can be validated on the patient population and be utilised to improve patient pathway for HFpEF.
- Follow patients up over one year to monitor outcomes

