8. STUDY DESIGN

8.1 Summary of Study Design

Data will be collected retrospectively from consecutive patients who meet the inclusion criteria to calculate a H2FPEF score: weight, number of hypertensive medications prescribed, presence of AF or not, presence of pulmonary hypertension or not, age and filling pressure. A total H2FPEF score will then be calculated for each patient as per Reddy et al. (2018) protocol: BMI > 30 kg/m² (2 points), ≥2 anti-hypertensive medications (1 point), paroxysmal or permanent AF (3 points), pulmonary artery systolic pressure >35mmHg (1 point), age >60 years (1 point), E/e' filling pressure > 9 (1 point).

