8.2 Primary and Secondary Outcome Measures

Primary outcome measure

- Accuracy of H2FPEF at predicting HFpEF on the patient population will be assessed as specificity and sensitivity as calculated by logistic regression

Secondary outcome measure

- Investigate if H2FPEF overestimates HFpEF diagnosis on the patient population when compared against known BNP levels.
- To evaluate if H2FPEF can be validated on the patient population and be utilised to improve patient pathway for HFpEF.
- To assess patient outcomes after one year, including any changes in medication or treatment as well as number of hospital admissions and reported symptoms.

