13.3 Procedure for Dealing with Missing, Unused and Spurious Data

Only data relating to the H2FPEF score will be collected; as per inclusion/ exclusion criteria no patient will be included in the study unless they had all of the necessary tests at their clinic visit. If no data is available for one year follow-up then the patient will be excluded from this assessment, but will still be included in the initial assessment of the H2FPEF diagnostic criterion.

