14.1 Participant Confidentiality

The study staff will ensure that the participants' anonymity is maintained. Only the relevant clinical data will be collected, and will only be accessed by members of the research team that are involved in the clinical care and would have access anyway. All documents will be stored securely on secured personal hospital drives with password protection and only accessible by study staff and authorised personnel. The study will comply with the Data Protection Act which requires data to be anonymised as soon as it is practical to do so.

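### Section 8.1 gives paroxysmal or permanent AF 3 of the 9 points, but the only means 11.4 names for AF status is the ECG, so documented paroxysmal AF in sinus rhythm can score 0

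*Combined protocol and SAP*

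**What the plan says.** Section 8.1 (Summary of Study Design) lists the six items and their points. The AF item is "paroxysmal or permanent AF (3 points", the largest weight of the six.

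Section 11.4 (Study Assessments) names six items to collect and then describes where they come from. Echocardiography supplies pulmonary and filling pressure, a scale supplies weight, and two items come from the notes: "Age and Number of hypertensive medications taken - Assessed from patient records". For AF it says: "ECG results will be used to determine if the patient is in AF or not". The opening of 11.4 gives the heart failure clinic database as the general source for all data.

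The form in 12.1 has one yes/no AF column, with no field for type or source. The clinical evaluation required by the inclusion criteria in 9.3 lists age, weight and medication count, but not AF history.

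The primary outcome in 8.2 is: "Accuracy of H2FPEF at predicting HFpEF on the patient population will be assessed as specificity and sensitivity". The same sentence says that these are obtained by logistic regression. No section states a cut-off for the score.

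**The concern.** The definition in 8.1 covers an arrhythmia that comes and goes. The ECG sentence in 11.4 describes the rhythm at one recording. A patient with documented paroxysmal AF who is in sinus rhythm at the ECG meets the first and fails the second. Permanent AF, and paroxysmal AF present at the recording, are scored correctly either way.

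Two extractors could each point to the protocol and differ by 3 points on the same patient, and the spreadsheet would not show which rule was used. The index test of an accuracy study would then not be the score that the plan defines. A larger sample does not remove an error of this kind.

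**Working it through.** **1. Weight of the item.** From 8.1, in the order BMI, medications, AF, PASP, age, E/e': 2 + 1 + 3 + 1 + 1 + 1 = 9. AF is 3/9 of the total, and the maximum without it is 6. If S (0 to 6) is the sum of the other five items, an affected patient scores S + 3 under 8.1 and S under the ECG rule.

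**2. Which profiles change sides.** The other five items have 2^5 = 32 yes/no profiles. For cut-offs 1 to 9, losing 3 points moves 1, 5, 12, 19, 22, 19, 12, 5 and 1 of the 32 from positive to negative. This count needs no assumed rates, but the profiles are not equally common in practice.

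**3. Effect at a fixed cut-off.** All rates here are assumptions. Prevalences of BMI, medications, AF, PASP, age and E/e' are .55, .65, .35, .50, .90, .70 in cases and .35, .50, .08, .25, .75, .40 in non-cases, independent given disease. A share m of AF is missed, equally in both groups.

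At a cut-off of 5, P(positive) = P(S ≥ 5) + AF rate × (1 − m) × P(2 ≤ S ≤ 4). Enumeration gives P(S ≥ 5) = 0.3466 and P(2 ≤ S ≤ 4) = 0.6175 in cases, and 0.0897 and 0.6909 in non-cases.

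- m = 0: sensitivity 0.3466 + 0.35 × 0.6175 = 0.563; specificity 1 − (0.0897 + 0.08 × 0.6909) = 0.855
- m = 0.05: 0.3466 + 0.3325 × 0.6175 = 0.552; 1 − (0.0897 + 0.076 × 0.6909) = 0.858
- m = 0.50: 0.3466 + 0.175 × 0.6175 = 0.455; 1 − (0.0897 + 0.04 × 0.6909) = 0.883

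At a cut-off of 3, sensitivity falls only from 0.890 to 0.887-0.860. With AF in 20% of cases and 5% of non-cases, sensitivity at 5 goes from 0.470 to 0.464-0.408; with 50% and 20%, from 0.655 to 0.640-0.501.

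**4. Effect when the threshold is refitted.** Section 8.2 obtains sensitivity and specificity from logistic regression. Assume a model of disease on score, classified at a predicted probability of 0.5 (the plan gives no threshold). The cut-off is the first whole score at or above −intercept/slope. With 30% cases, that point moves from 5.10 (m = 0) to 4.97 (m = 0.25), so the cut-off moves from 6 to 5. Sensitivity then rises from 0.364 to 0.509 and specificity falls from 0.948 to 0.869. The same reversal of sensitivity occurs with 45% cases and 25% missed (0.563 to 0.703), and with 60% cases and 50% missed (0.738 to 0.860).

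**5. Other summaries.** The odds ratio per point is about 1.91 with none missed and 1.90 with half missed, at 35-40% cases. AUC is 0.790 with none missed and 0.787-0.763 with equal miss shares of 5-50%. With unequal shares (cases/non-cases) it is 0.790 at 20%/50%, 0.802 at 10%/60% and 0.751 at 50%/20%.

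**6. What the fix recovers.** At a cut-off of 5, sensitivity regains 0.563 − 0.552 = 0.011 (m = 0.05) to 0.563 − 0.455 = 0.108 (m = 0.50) if all missed AF is documented. If half is documented, it regains 0.005 to 0.054.

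**The case against.** The strongest reply is that this is loose drafting, not a contradiction. Section 8.1 is the scoring rule. The ECG sentence sits in a list describing routine tests, and that list is not a complete account of sources, since height and BNP have none. It does not say that the ECG is the only source, and the clinic database may hold an AF diagnosis. The yes/no column proves little, because every item on the form looks the same. A reader might infer that the plan deliberately discards AF history; the documents do not support that. What remains is that each of the six items listed in 11.4 is given a source, that AF's is the ECG, and that nothing says how to code recorded AF with a sinus-rhythm tracing.

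A reader might also infer that the error must bias the study against its own secondary objective: "Investigate if H2FPEF overestimates HFpEF diagnosis on the patient population when compared against known BNP levels". At a fixed cut-off, false positives among non-cases do fall, from 14.5% to 14.2%-11.7% in the illustration. But the plan fixes no cut-off, and in the 30%-case example with a refitted model they rise from 5.2% to 13.1%. The direction is conditional.

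Two further points stand. The planned odds ratio hardly moves when AF is missed equally in both groups. And the ECG is required of every participant, so it is a uniform source, whereas history may be recorded more fully in cases than in non-cases, or the reverse.

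**Conclusion.** The mismatch is real and should be settled before extraction. Following 11.4 gives a wrong value, by the plan's own definition in 8.1, for any patient with documented paroxysmal AF in sinus rhythm.

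The direction is certain only at a fixed score cut-off. It can reverse with a refitted model threshold, and for AUC it depends on whether the share missed differs between cases and non-cases.

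The size cannot be derived from the documents. On the assumed rates it is negligible at a low miss share or a low cut-off. It is moderate, about 0.11 of sensitivity, only if about half of AF is missed and the cut-off is around 5. Confidence is medium, because extractors may in practice apply 8.1 to the database.

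**What to change.** Reconcile 11.4 and 12.1 with 8.1. State that AF is scored as present if paroxysmal or permanent AF is documented in the clinic database or patient record up to the index visit, or is present on the index ECG. Add a column for the source (history, ECG or both), and report a sensitivity analysis that scores AF from the ECG alone.

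The cost is two wording changes, one column and slightly more extraction time. The patient records are already a named source for the medication count, and 14.1 says the data "will only be accessed by members of the research team that are involved in the clinical care and would have access anyway". AF history feeds the score, so it fits the limit in 13.3: "Only data relating to the H2FPEF score will be collected".

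The downside is that recorded history may be incomplete, so undocumented paroxysmal AF stays missed. It may also be recorded unequally in cases and non-cases. The source column and the ECG-only analysis would show how far the results depend on it.

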12. DATA HANDLING AND RECORD KEEPING

12.1 Data Collection Forms

All data will be collected and stored electronically using the following format.

Participant ID	BMI (>30Kg/m ²) Yes/No	≥2 anti-hypertensive medications Yes/No	AF Yes/No	PASP >35mmHg Yes/No	Age (>60 years) Yes/No	E/e' (>9) Yes/No	H2FPEF Score	Patient Outcomes

12.2 Data Management

Data management will be conducted by the investigators using clinical, access databases and excel documents. All study data obtained will be documented electronically on a Microsoft Excel document on a personal Trust drive at the investigator site and will be accessible only by the research team. Data will be monitored at the investigator site. The participants will be identified by a study specific participants number and/or code in any database. The name and any other identifying detail will not be included in any study data electronic file.

13. DATA ANALYSIS

13.1 Description of Analysis Populations

All eligible participants will be analysed the same as per protocol.

13.2 Analysis of Outcome Measures

To determine if the H2FPEF score was accurate in predicting HFpEF the calculated H2FPEF score will be compared against BNP blood test results using the cut-off points stated by the European Society of Cardiology (Ponikowski et al., 2016). To test our hypothesis an analysis of variance test (ANOVA) will be performed to provide one simultaneous evaluation of the data to determine if there is a significant difference between H2FPEF score and diagnosis of HFpEF. A logistic regression analysis will then be carried out to give an odds ratio and provide a predictive analysis of the data. All statistical analysis will be performed using SPSS software.

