HFpEF was previously characterised as ‘diastolic dysfunction’ but this terminology was changed as it was found that diastolic dysfunction was also seen in patients with ‘systolic dysfunction’ (Borlaug and Paulus, 2011). Myocardial stiffness which leads to increased filling pressures is a common pathophysiologic attribute of HFpEF despite its multifactorial aetiology (Telles and Marwick, 2018). Other common conditions associated with HFpEF include: atrial fibrillation (AF), chronotropic incompetence, pulmonary hypertension, right ventricular dysfunction and endothelial dysfunction; with common non-specific risk factors such as: age, gender, hypertension, obesity, diabetes, metabolic syndrome and renal failure (Borlaug, 2014; Ferrari et al., 2015; Harper et al., 2018). This complex heterogeneity of HFpEF which is not yet fully understood highlights the difficulty that clinicians have in being able to diagnose the condition.

Diagnosis of HFpEF is difficult and as of yet there is no test to confirm diagnosis, with current guidelines saying initial diagnosis should include the presence of typical signs and symptoms, an elevated B-type natriuretic peptide (BNP) (>35 pg/mL and/or N-Terminal pro-

B-type Natriuretic Peptide [NT-proBNP] >125 pg/mL) and ejection fraction $\geq 50\%$ (Lekavich et al., 2015; Ponikowski et al., 2016). Echocardiography is the preferred method of assessing for HFpEF due to it being widely available, non-invasive, and able to provide immediate results (Ponikowski et al., 2016). Recent studies comparing the use of echocardiography against 'gold standard' invasive cardiac catheterisation to assess cardiac filling pressures found echocardiography to be just as accurate and reliable (Anderson et al., 2017; Lancellotti et al., 2017). Implications of this research would be that patients could be assessed as outpatients by focus echocardiography rather than invasively in the cardiac catheterisation lab, which would improve patient experience, enhance patient outcomes and prove cost-effective for trusts.

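### If AF and obesity shift BNP apart from HFpEF, a peptide reference that ignores both, set against a score taking 5 of its 9 points from them, can hide opposite errors in one pooled accuracy figure

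*Combined protocol and SAP*

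**What the plan says.** Section 13.2 sets the comparison for accuracy: "To determine if the H2FPEF score was accurate in predicting HFpEF the calculated H2FPEF score will be compared against BNP blood test results", at the European guideline's cut-offs. Section 5 (Background) gives those cut-offs as BNP above 35 pg/mL and/or NT-proBNP above 125 pg/mL, with no version by AF or BMI. Section 11.4 brings in one more element: "In addition the patient's ejection fraction and BNP will also be recorded as a measure to determine HFpEF diagnosis". A secondary objective in section 7.2 uses the same yardstick: "Investigate if H2FPEF overestimates HFpEF diagnosis on the patient population when compared against known BNP levels".

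Section 8.1 gives the score weights: "BMI > 30 kg/m² (2 points), ≥2 anti-hypertensive medications (1 point), paroxysmal or permanent AF (3 points") and "pulmonary artery systolic pressure >35mmHg (1 point), age >60 years (1 point), E/e' filling pressure > 9 (1 point").

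Section 13.1 has all eligible patients analysed alike. No stratum, adjustment or caveat for AF or BMI appears anywhere. Section 5 links AF and obesity to HFpEF but does not say that either changes BNP by another route.

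**The concern.** Sensitivity and specificity against an imperfect reference are easiest to interpret when, given true disease status, errors in the reference are unrelated to the test. That may fail here. Suppose AF raises BNP in patients without HFpEF. Such a patient gains 3 points and is more likely to pass the cut-off, so the score is credited. Suppose obesity lowers BNP in patients with HFpEF. Such a patient gains 2 points and is more likely to fall below the cut-off, so a high score counts as a false positive.

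The second error points the same way as the investigators' hypothesis that the score overestimates HFpEF; the first points towards validation. Section 5 (Impact) lets the overall answer decide whether the score counts as validated or needs to be optimised or replaced. One pooled comparison cannot show how much of that answer comes from these two items.

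**Working it through.** **Step 1: the score.** From section 8.1: 2 + 1 + 3 + 1 + 1 + 1 = 9 points. AF and BMI give 3 + 2 = 5, and 5/9 = 56%. The other four items total 4. Possible scores are therefore 0–4 with neither item, 2–6 with BMI only, 3–7 with AF only and 5–9 with both.

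**Step 2: the plan's own figures.** The only planning figure is a sample size of 2000, given without derivation, so there is nothing to reproduce. The point does not depend on it.

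**Step 3: an illustration.** Only the weights and the cut-off of 35 pg/mL come from the documents. Everything else is assumed:
- True HFpEF in 50%; BNP log-normal, median 25 without and 80 with HFpEF, log SD 0.9.
- Item prevalence without/with HFpEF: BMI 35/50%, antihypertensives 50/70%, AF 10/30%, PASP 25/50%, age 60/80%, E/e' 40/70%; items independent given disease status.
- AF multiplies BNP by a (1 to 3); obesity multiplies it by b (0.5 to 1).

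For each of the 64 item patterns in each disease group, P(BNP > 35) = 1 − Φ[(ln 35 − ln median − AF·ln a − obese·ln b)/0.9]. The AUC is P(score higher in a reference-positive than in a reference-negative patient) + ½ P(tie).

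Two single cells show the mechanism:
- No HFpEF, not obese: P(BNP > 35) is 0.354 in sinus rhythm. With AF and a = 2 it is 1 − Φ[(ln 35 − ln 50)/0.9] = 0.654.
- HFpEF, no AF: P(BNP > 35) is 0.821 if not obese. If obese with b = 0.65 it is 1 − Φ[(ln 35 − ln 52)/0.9] = 0.670.

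**Step 4: pooled results.** AUC against true HFpEF is 0.765 throughout.

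| AF effect a | Obesity effect b | AUC against BNP |
|---|---|---|
| 1 | 1 | 0.628 |
| 1.5 / 2 / 3 | 1 | 0.663 / 0.681 / 0.699 |
| 1 | 0.8 / 0.65 / 0.5 | 0.601 / 0.575 / 0.541 |
| 1.5 | 0.8 | 0.637 |
| 2 | 0.65 | 0.634 |
| 3 | 0.5 | 0.628 |
| 3 | 0.8 | 0.677 |
| 1.5 | 0.5 | 0.580 |

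At an illustrative threshold of 4 or more (the plan states none), sensitivity/specificity are 56.8/61.7% with no effect, 59.0/67.2% with AF x2 alone, 53.8/55.9% with obesity x0.65 alone and 57.0/60.9% with both. With 1000 reference-positive patients, the 95% half-width at 60% sensitivity is 1.96·√(0.6·0.4/1000) = 3.0 points. The one-sided shifts of about 2 to 6 points are similar to or larger than that; the combined shift is smaller.

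**Step 5: strata, at a = 2 and b = 0.65, against no effect.**
- No AF (obese patients remain): AUC goes from 0.610 to 0.547.
- BMI 30 or below (AF patients remain): AUC goes from 0.626 to 0.683.

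These are also what a clinic with no AF, or with no obesity, would see as its pooled result, so the mix matters. In the four cross-classified cells both items are constant and cannot by themselves link score to reference. The AUCs there are 0.611 (neither), 0.621 (BMI only), 0.636 (AF only) and 0.605 (both).

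**Step 6: score without AF and BMI.** With those weights set to 0, the AUC against BNP is 0.622 with no effect and 0.611 to 0.625 over the combined scenarios above. It is 0.605 to 0.628 if the one-sided scenarios are included. The full score ranges from 0.541 to 0.699 over the same set.

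**The case against.** The premise is not in the documents. Section 5 ties AF and obesity to HFpEF, not to BNP by a separate route. That stands, so the point has to be conditional and shown over a range that includes no effect.

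The reference is also more than a single BNP cut-off: there is an NT-proBNP value, section 11.4 adds ejection fraction, and the definition in section 5 includes signs and symptoms. This softens the point without removing it. Both peptide cut-offs ignore AF and BMI. Among patients with ejection fraction of 50% or more, the peptide is what separates cases from non-cases. Section 11.4 does not name symptoms among the measures that determine diagnosis.

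The strongest objection concerns size. With both effects at middling values the pooled figure hardly moves (56.8/61.7% to 57.0/60.9%), well inside sampling error. The larger loss, from 0.765 to 0.628, comes from BNP being an imperfect reference for everyone, and stratifying does not cure that. Both statements stand. A reader might infer that pooled accuracy will be inflated by AF, or that a finding of overestimation would be an artefact of obesity. The documents support neither reading, because the net shift has no fixed sign. But a small net shift can be the sum of two opposite errors, which the planned analysis could not reveal.

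Finally, section 5 speaks of potential use and of further research either way, so the pooled result is not an automatic adoption rule.

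**Conclusion.** The point holds in a limited form. The documents establish a peptide reference that does not vary by AF or BMI, 5 of 9 points on those two items, and no analysis by either. If AF raises and obesity lowers BNP independently of HFpEF, the AUC against BNP moves from 0.628 up to 0.699 (AF alone) or down to 0.541 (obesity alone) over the assumed range. With both, it lies on either side of 0.628 or cancels. The pooled figure would then depend on the hospital's AF and obesity mix and could hide opposite errors. The sizes rest on the assumed prevalences, BNP distributions and multipliers in the working.

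A reader might also infer that patients without AF, or those with BMI 30 or below, give the clean answer. They do not: each group keeps the other bias. Patients with neither item can score at most 4, so they cannot carry the conclusion alone. This is an inexpensive improvement to the analysis and does not prevent the study from running.

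**What to change.** In section 13.2:
- State the score threshold for sensitivity and specificity in advance.
- Next to the pooled result, report AUC with confidence intervals, and sensitivity and specificity at that threshold, in the four AF-by-BMI cells. Give the AUC more weight: score ranges differ by cell, and a threshold of 5 or less classes every patient with both items as positive.
- Add a sensitivity analysis of the score without the AF and BMI items.
- State that a pooled conclusion of overestimation or validation will be qualified if the cells and the reduced score do not support it. Do not make the conclusion depend on the no-AF or BMI 30-or-below groups.
- State the limits of a natriuretic-peptide reference.

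Reconcile sections 12.1 and 13.3 with 11.4. The collection form has no column for BNP or ejection fraction, and 13.3 restricts collection to score data, yet 11.4 says both will be recorded. The tables cannot be built without them.

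The cost is a few extra tables; AF and BMI are already on the form. The downside is precision. In the illustration the smallest cell holds 9.25% of 2000 = 185 patients. The AF-only cell has 215 patients, of whom about 215 × (1 − 0.864) = 29 are reference-negative. The half-width for a specificity of 50% there is 1.96·√(0.25/29) = 18 points, so the cells should be read as descriptive.
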